4. GENERAL STATISTICAL CONSIDERATIONS

This SAP was developed based on International Council on Harmonization (ICH) E3 and E9 Guidelines. This SAP should be read in conjunction with the study protocol and electronic case report forms.

Unless otherwise noted, the summary of continuous variables will include the number of nonmissing observations (n), arithmetic mean, median, standard deviation (SD), minimum, and maximum. Percentages will be calculated using the number of subjects within group and overall as the denominator.

All statistical analyses will be conducted using SAS[®] software (Version 9.4 or higher, SAS Institute Inc., Cary, NC).

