4.3. Randomization and Stratification

Subjects will be randomized after the Investigator has verified that they are eligible per criteria in Section 3.5 and Section 3.6 of the protocol. Subjects will then be enrolled into this study and assigned to APD371 25 mg TID or 100 mg TID according to a randomization schedule. Randomization will be stratified by sex.

Randomization will take place across all study sites using a centralized master list held by the Sponsor clinical trial manger, in consultation with the Medical Monitor. When a site is ready to

Statistical Analysis Plan APD371-004

enroll a subject, they will contact the study manager to get the appropriate dose group assignment and unique subject number. The subject's identification number will be used on all of that subject's electronic case report forms (eCRF). Any subject identification numbers that are assigned will not be reused even if the subject does not receive treatment. All subjects must start treatment within 1 week of randomization.

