8.1. Abdominal Pain Score (APS)

For each subject, APS score measured at peak will be averaged over the entire treatment period. Likewise, the APS score measured at trough will be averaged for each subject. The difference (peak - trough) will be calculated, per subject, as mean (peak) - mean (trough).

Mean peak, trough, and peak - trough will be summarized by treatment and overall. The peak - trough differences will be analyzed between treatments using an analysis of covariance (ANCOVA) model with treatment as a factor and Baseline score as a covariate. The 95% CI for the adjusted treatment difference will be presented together with the p-value. For the pooled data, a 1-sample t-test will be conducted testing against the hypothesis of zero difference between peak and trough. The 95% CI for the overall difference between peak and trough assessments will be presented.

Additionally, the APS score measured prior to evening dose (evening trough) will be averaged for each subject. The difference (peak - evening trough) will be calculated, per subject, as mean (peak) - mean (evening trough). The analysis will be repeated using mean peak, evening trough, and peak - evening trough and will be summarized by treatment and overall.

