8.2. Average Abdominal Pain Score (AAPS)

AAPS is the average of the APS score over each weekly assessment period (Wks 1, 2, 4, 6, 8). The Baseline value of AAPS will be derived as the average of the last (most recent) non-missing 7 days of morning and evening diary records within the Screening period prior to Day 1 of treatment. During the treatment period, summaries for a nominal week will be derived from the last 7 days within that period that contain a non-missing assessment. Summaries may be derived from fewer than 7 days (e.g., if the Wk 1 and Wk 2 Visits are less than 7 days apart). AAPS will be summarized for the Screening period and for each assessment week of treatment before morning dose (trough) assessments and 1.5 hours post-treatment first daily dose (peak) assessments, by treatment group and overall. Statistical comparisons of AAPS will be made between Screening and Wk 4 and Wk 8, trough and peak assessments, by treatment and overall. Change scores from Baseline for peak and trough at Wk 4 and Wk 8 will be derived. Treatment comparisons of the change scores will be analyzed using ANCOVA as for AAPS. The adjusted

treatment effect, 95% CI, and p-value will be presented. Overall changes from Baseline at Wk 4 and Wk 8 will be assessed using 1-sample t-tests as for AAPS. These analyses will be repeated for the Per Protocol population.

Peak and trough AAPS by treatment and visit will be plotted displaying treatment means and 95% CIs for the efficacy population only.

These analyses will be repeated where AAPS will be summarized for the Screening period and for each assessment week of treatment before evening dose (evening trough) assessments and 1.5 hours post first daily dose (peak) assessments, by treatment group and overall.

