8.6. C-reactive protein (CRP)

CRP will be summarized by visit (Baseline, Wk 4, Wk 8). Within subject changes from Baseline at Wk 4 and Wk 8 will be analyzed by treatment and overall using dependent means t-tests. Mean change, 95% CIs and p-values will be presented. Changes from Baseline at Wk 4 and Wk 8/EOT will be analyzed using an ANCOVA model with treatment as a factor and Baseline value as a covariate. Adjusted treatment effects with p-values and 95% CIs will be presented. CRP by treatment and visit will be plotted for the Efficacy population displaying treatment means and 95% CIs. A scatterplot will be produced of change from Baseline in CRP and change from Baseline in peak AAPS at Wk 8 for all subjects (irrespective of treatment) in the Efficacy population. A regression line will be fitted.

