8.7. Fecal Calprotectin

Fecal calprotectin will be summarized by visit (Baseline, Wk 4, Wk 8). Within subject changes from Baseline at Wk 4 and Wk 8 will be analyzed by treatment and overall using dependent means t-tests. Mean change, 95% CIs and p-values will be presented. Changes from Baseline at Wk 4 and Wk 8 EOT will be analyzed using an ANCOVA model with treatment as a factor and Baseline value as a covariate. Adjusted treatment effects with p-values and 95% CIs will be presented. Fecal calprotectin by treatment and visit will be plotted for the efficacy population displaying treatment means and 95% CIs. A scatterplot will be produced of change from Baseline in fecal calprotectin and change from Baseline in peak AAPS at Wk 8 for all subjects (irrespective of treatment) in the Efficacy population. A regression line will be fitted.

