- Figure 14.2.6. Mean Fecal Calprotectin by Treatment and Visit (Efficacy Population)
- Figure 14.2.7. Scatterplot of Changes from Baseline in Peak AAPS and Fecal Calprotectin at Week 8 (Efficacy Population)
- Figure 14.2.8. Scatterplot of Changes from Baseline in Peak AAPS and C-Reactive Protein at Week 8 (Efficacy Population)
- Figure 14.3.4.1. Active Standing Test Vital Signs by Treatment and Visit (Safety Population)
- Figure 14.3.4.2. Active Standing Test Vital Signs by Treatment and Visit Alternate (Safety Population)
- Figure 14.3.4.3. Individual Subject Active Standing Test Vital Sign Profiles (Safety Population)
- Figure 14.3.4.4. Individual Subject Active Standing Test Vital Sign Profiles Day 1 (Safety Population)

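### Minor: the between-dose ANCOVAs leave out the sex stratum (a precision cost only), and the untransformed CRP and calprotectin intervals may under-cover if those markers are skewed

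*SAP*

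**What the plan says.** **Sex.** SAP 4.3 states: "Randomization will be stratified by sex". SAP 8.1 compares the peak-minus-trough pain difference between doses "using an analysis of covariance (ANCOVA) model with treatment as a factor and Baseline score as a covariate". SAP 8.2 says of the weekly averages: "Treatment comparisons of the change scores will be analyzed using ANCOVA as for AAPS". That cross-reference points to its own section, so I read it as meaning the model in 8.1. In SAP 8.6, CRP changes are "analyzed using an ANCOVA model with treatment as a factor and Baseline value as a covariate", and SAP 8.7 gives calprotectin the same model. None of these models has a sex term.

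Sex appears elsewhere only as a subgroup. Protocol 8.1 commits to a subgroup analysis by sex, SAP 10.2 makes it optional, and SAP 13 lists Table 14.2.2.3, weekly average pain by sex for all subjects.

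**Markers.** Within-subject changes in calprotectin "will be analyzed by treatment and overall using dependent means t-tests" (SAP 8.7), and SAP 8.6 does the same for CRP. Neither section names a transformation or a non-parametric alternative, although Protocol 8.1 leaves both parametric and non-parametric methods open. The only transformation sentence, in Protocol 8.5, concerns pharmacokinetics.

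**The concern.** A model that ignores a stratification factor leaves any variation due to that factor in the residual. With about 8 subjects per dose, intervals are wide already, so a cheap gain in precision is worth looking at.

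The marker question is different. Concentrations such as these may be right-skewed, and a t-interval for a raw mean change can be unreliable at n = 8 or 16 when the change itself is skewed. Reduction in CRP and calprotectin is a stated exploratory objective (SAP 2.2), and mean changes with 95% CIs and p-values will be reported. What is at stake is how those effect sizes are read. No primary conclusion depends on them, because SAP 3.3.1 names no primary endpoint.

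**Working it through.** The plan gives no SD, effect size, correlation or power figure, so there is no stated result to reproduce. From the documents: 16 subjects, 8 per dose, 1:1, stratified by sex, two-sided 95% intervals. All other inputs below are assumptions shown over a range.

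**1. Cost of leaving out sex**

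Let g be the male-female gap in residual SDs after Baseline adjustment. With 8 of each sex, balanced across doses, omitting sex adds (8 × 8 / 16)g² = 4g² to the residual sum of squares, in units of the residual variance. The planned model has 16 − 3 = 13 residual df; adding sex leaves 12. The approximate ratio of half-widths, with sex over without, is

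t(0.975, 12) / [t(0.975, 13) × √(1 + 4g²/13)], with t-values 2.179 and 2.160 (ratio 1.0085).

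| g | √(1 + 4g²/13) | Formula | Simulation |
|---|---|---|---|
| 0 | 1.000 | +0.9% | +1.0% |
| 0.5 | 1.038 | −2.8% | −2.5% |
| 1.0 | 1.144 | −11.8% | −11.0% |

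In the simulation the planned interval covered 95.1% to 97.0%, with no bias. With 4 of one sex and 12 of the other, simulated changes were +1.0%, −1.7% and −8.4%. Break-even with 8 per sex is near a gap of 0.26 SD.

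**2. Raw-scale marker intervals**

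Model: lognormal Baseline and follow-up values with a given log-SD and log-scale correlation. For a fall f with equal spread, the true mean change is −f × exp(SD²/2). Each run counts how often the 95% interval contains it.

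Paired t, log-SD 1.0, equal spread:

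| n, correlation | No change | 10% fall | 20% | 30% | 50% |
|---|---|---|---|---|---|
| 8, 0.5 | 97.4% | 96.9% | 95.7% | 93.6% | 88.5% |
| 8, 0.7 | 97.5% | 96.9% | 94.6% | 91.7% | 85.9% |
| 8, 0.85 | 97.6% | 96.1% | 92.4% | 88.5% | 83.2% |
| 16, 0.7 | 96.7% | 96.3% | 94.7% | 92.2% | 87.8% |

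At correlation 0.95 and n = 8, a 10% fall already gives 93.6%. With little skew (log-SD 0.2), paired-t coverage stays at 94.3% to 95.4% throughout.

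Between-dose ANCOVA (8 v 8, log-SD 1.0, correlation 0.7): 96.5%, 96.0%, 95.1%, 93.6% and 88.1% at dose differences of 0, 10, 20, 30 and 50%.

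**3. Direction of the misses**

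With equal spread and no change, the two skewed distributions offset each other, the difference is symmetric, and the t-test is conservative. With a fall, the long Baseline tail is no longer offset. Samples that happen to lack an extreme Baseline value then show both a small fall and a small SD. At a 30% fall (n = 8, log-SD 1.0, correlation 0.6), 6.8% of intervals lay wholly above the true change and 0.3% wholly below it. Most misses therefore understate the fall.

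**4. Unequal spread with no change in mean**

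- Log-SD rising from 0.7 to 1.0 (correlation 0.6): coverage 92.4% to 93.1%, and a false fall declared in 6.7% to 7.3% of trials against a nominal 2.5%.
- Log-SD shrinking from 1.0 to 0.7 (n = 8, correlations 0.3 to 0.85): coverage 94.3% down to 88.1%.
- ANCOVA with equal means but log-SD 0.7 or 0.5 instead of 1.0 at one dose: 93.2% or 87.5%.

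**5. Log scale**

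At log-SD 1.0 and correlation 0.7, log-ratio intervals covered 94.8% to 95.2%. This is expected, because the data were generated as lognormal. In the opposite case, with additive normal changes (30% mean fall, n = 16, CV 0.4), the log analysis has 78% power against 88% for the raw test.

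**The case against.** The planned two-term ANCOVA is valid. A reader might infer that ignoring the stratum biases the dose contrast or inflates type I error. Neither follows: randomisation balances sex across doses, and the effect of omission is conservative. The documents do not say that sex is prognostic, and with 16 subjects a smaller model is defensible. That stands, and it is why the point is minor. The sex subgroup provisions are relevant but do not answer it. By its title, the by-sex table describes all subjects and does not adjust the dose comparison.

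The marker point is hypothetical, because the documents give no distribution, SD, correlation or expected change. That also stands. A reader might take 30% as a fixed threshold below which the raw intervals are safe. The documents supply no such threshold, and it moves with correlation and spread. A reader might also infer that the raw tests cannot produce a false claim of benefit because they are conservative when nothing changes. That holds only if spread is also unchanged.

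The SAP does offer partial safeguards. Its default summaries are "arithmetic mean, median, standard deviation (SD), minimum, and maximum" (SAP 4). SAP 8.6 adds: "A scatterplot will be produced of change from Baseline in CRP" against change in peak pain, and SAP 13 lists the calprotectin counterpart, "Scatterplot of Changes from Baseline in Peak AAPS and Fecal Calprotectin". SAP 8 warns that inference may be inappropriate if numbers are very low. These help show outliers or limit inference, but they do not correct the reported intervals.

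**Conclusion.** Both parts hold as minor points in an exploratory study.

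The sex omission is a matter of precision alone: about 2.5% of interval width at a 0.5 SD gap and 11% at 1.0 SD with 8 per sex, against about 1% lost if sex is irrelevant. The size depends on an unknown sex effect; the absence of bias does not.

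The marker part is secondary and conditional. Given right skew, raw-scale intervals under-cover mainly at true falls or dose differences of about 20-30% or more (less at high correlation between Baseline and follow-up), or when spread changes over time or differs between doses. With a true fall and equal spread, the misses mostly understate the fall. With no mean change and rising spread, a false fall can be declared more often than nominal. Nothing in the documents shows that these conditions apply here.

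**What to change.** Keep every planned analysis.

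1. Add sex as a factor to the between-dose ANCOVAs in SAP 8.1, 8.2, 8.6 and 8.7, and report the results beside the planned models in the Efficacy population. Label them post hoc, because SAP Amendment 1 itself postdates database lock. This uses collected data only and costs one residual df (13 to 12) in about 12 models: 2 for the daily pain score, 6 for the weekly average, 2 for CRP and 2 for calprotectin.

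2. Optionally, add a log-ratio-to-Baseline sensitivity analysis for CRP and calprotectin, with log Baseline as the ANCOVA covariate, giving geometric mean ratios with 95% CIs within dose, overall and between doses. State that it estimates a ratio instead of a mean difference and loses power if changes are additive. Show both scales side by side; plots of about 16 subjects are too thin a basis for choosing between them. The further cost is more unadjusted post hoc intervals in a small study, so item 1 has priority.

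### The overall pain, CRP and calprotectin tests leave randomised dose out of the error term, so their intervals are conservative if the doses differ (minor, exploratory)

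*SAP*

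**What the plan says.** SAP 4.2 allocates subjects 1:1 to 100 mg TID or 25 mg TID, and protocol 3.1 plans 8 per cohort.

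- **SAP 8.1 (peak minus trough APS).** The doses are compared with an "analysis of covariance (ANCOVA) model with treatment as a factor and Baseline score as a covariate". The overall result is separate: "For the pooled data, a 1-sample t-test will be conducted testing against the hypothesis of zero difference between peak and trough", and "The 95% CI for the overall difference between peak and trough assessments will be presented".
- **SAP 8.2 (AAPS).** "Overall changes from Baseline at Wk 4 and Wk 8 will be assessed using 1-sample t-tests as for AAPS". Since this sentence stands in the AAPS section, its cross-reference points to itself. I read it as pointing to the APS method in 8.1.
- **SAP 8.6 (CRP), with the same wording in 8.7 (fecal calprotectin).** "Within subject changes from Baseline at Wk 4 and Wk 8 will be analyzed by treatment and overall using dependent means t-tests", with mean change, 95% interval and p-value. Each section also plans a scatterplot of biomarker change against change in peak AAPS, with a fitted line, "for all subjects (irrespective of treatment) in the Efficacy population".

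Treatment is a factor in the between-dose ANCOVAs of all four sections and in none of the overall tests. SAP 4.6 makes all of this exploratory, with estimates and intervals as the basis for interpretation.

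**The concern.** The pooled data are two fixed groups at a four-fold difference in assigned dose. A one-sample t-test takes its SD around the single pooled mean, so a true gap between the dose means is counted as noise. With no placebo arm and about 16 subjects, the pooled change is the tightest efficacy estimate that the trial can offer, and it loses precision in just the situation the design allows for, a dose response.

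The scatterplots ignore the same grouping. If dose moves both pain and the biomarker, one line through all points slopes even when the two are unrelated within each dose.

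**Working it through.** **Inputs.** Arms of 8 and 8 (protocol 3.1); two-sided 95% intervals (protocol 8.1). SAP 4.1 reports no power calculation and the documents give no SD, effect size or interval width, so there is no stated figure to reproduce. The dose difference d, in within-dose SDs (σ), is assumed over 0 to 2.

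**Step 1: variance seen by the pooled test.** With arm sizes n1 and n2 and n = n1 + n2,

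E(s²) = σ² × [1 + (n1·n2/n) × d²/(n − 1)].

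At 8 + 8, n1·n2/n = 64/16 = 4 and 4/15 = 0.267, so the inflation is 1 + 0.267d². With arm sizes fixed, the true variance of the overall mean is still σ²/n.

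**Step 2: width against a model with a treatment term.** The comparator is the same mean with within-dose variance on n − 2 = 14 df.

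Ratio = √(1 + 0.267d²) × t(0.975, 15)/t(0.975, 14) = √(1 + 0.267d²) × 2.1314/2.1448.

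Coverage is from 200,000 simulated trials per setting. Power is pooled versus with dose in the model, for an assumed overall change of 0.6 SD.

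| d | Variance inflation | Width ratio | Coverage, pooled | Power |
|---|---|---|---|---|
| 0 | 1.000 | 0.994 | 95.0% | 61% v 61% |
| 0.5 | 1.067 | 1.026 | 95.7% | 59% v 61% |
| 1.0 | 1.267 | 1.118 | 97.0% | 51% v 61% |
| 1.5 | 1.600 | 1.257 | 98.5% | 41% v 61% |
| 2.0 | 2.067 | 1.429 | 99.4% | not run |

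With the treatment term, simulated coverage stays at 95% throughout. At d = 1 the width ratio is 1.120 for 10 + 10 and 1.115 for 6 + 8.

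**Step 3: break-even.** The ratio is 1 when 1 + 0.267d² = (2.1448/2.1314)² = 1.0126, so d = √(0.0126/0.267) ≈ 0.22. Below that, the pooled interval is up to 0.6% narrower.

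**Step 4: unequal arms, 8 and 5 evaluable.** The pooled mean weights the doses 8/13 = 0.62 to 5/13 = 0.38, so at d = 1 it lies (0.615 − 0.5) × 1 = 0.115 SD from the equally weighted mean.

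Equal weights with a common SD and d = 0 give an expected width ratio of

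[½√(1/8 + 1/5)] / [1/√13] × t(0.975, 11)/t(0.975, 12) = 0.2850/0.2774 × 2.2010/2.1788 = 1.038.

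Now let the smaller arm have twice the other's SD (1 and 2), for which the common variance estimate averages (7×1 + 4×4)/11 = 2.09.

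- *Equal weights:* true variance ¼(1/8 + 4/5) = 0.231; the common-SD formula gives 2.09 × ¼ × 0.325 = 0.170.
- *Subject weights:* true variance (8×1 + 5×4)/169 = 0.166; the formula gives 2.09/13 = 0.161.

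The shortfall therefore falls mainly on the equally weighted interval. Its simulated coverage is about 92.5% at an SD ratio of 1.5 and about 90.4% at 2, while the planned pooled test keeps about 95%.

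**Step 5: scatterplot.** With no within-dose association and the doses differing by d on both variables, the pooled correlation at 8 + 8 is roughly 0.267d²/(1 + 0.267d²). At d = 1 that is 0.267/1.267 = 0.21, which agrees with the simulated mean.

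**The case against.** The case for leaving the plan alone is substantial.

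- **The error is on the safe side.** A reader might infer that the overall p-values are invalid. They are not: the pooled test over-covers, and at 8 + 8 the point estimate is identical. This stands.
- **Dose is handled elsewhere.** The same sections summarise by treatment and run between-dose ANCOVAs; 8.6 and 8.7 add paired tests by treatment. If the doses differ by 1 SD or more, an average across them matters less. This stands as a limit on importance, but the overall interval would still be reported and still be too wide.
- **No slope test is planned.** A reader might take the fitted lines as a test with an inflated error rate. The SAP specifies a line only, with no correlation, slope test or p-value, so the risk is one of visual interpretation.
- **Weighting is a choice.** It is tempting to call the pooled mean biased when one arm loses more subjects. It estimates a subject-weighted average; equal weighting is a different estimand. Neither is wrong, but only the second stays put under unequal dropout.
- **The remedy has costs.** With equal weights and a common SD, unequal arms can turn a conservative interval into one that under-covers (step 4). This stands and shapes the fix.
- **Weight and reach.** There is no primary endpoint (SAP 3.3.1), and inference may be dropped if numbers are very low (SAP 8). The change from Baseline is uncontrolled in subjects selected for AAPS of at least 4, so regression to the mean may matter more than width. Tables 14.2.10 and 14.2.11 are titled by treatment only, so it is unclear whether overall CRP and calprotectin results will be shown; AAPS has an all-subjects table (14.2.2.1).

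**Conclusion.** The point holds as a minor one about efficiency. If the doses differ, the overall intervals in SAP 8.1, 8.2, 8.6 and 8.7 are wider than the randomised design requires: about 3%, 12% and 26% at assumed differences of 0.5, 1 and 1.5 within-dose SD with 8 per arm. The cost is power, not false positives, and below about 0.22 SD nothing is gained by a change. These figures rest on normal data, a common within-dose SD, fixed arm sizes and dose differences that the documents do not supply. The scatterplot line can reflect dose alone, with a mean pooled correlation of about 0.2 at an assumed 1 SD effect on both variables.

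**What to change.** 1. **Overall tests (SAP 8.1, 8.2, 8.6, 8.7).** Estimate the overall mean change and its 95% interval from a model with treatment as a factor, using within-dose variance (14 df at 8 + 8).
2. **Weighting.** State it before the analysis is run. Subject weights keep the planned estimate; equal weights target the simple average of the two doses and do not shift with dropout.
3. **Unequal evaluable arms.** Use separate within-dose variances with Welch/Satterthwaite degrees of freedom in place of a common SD.
4. **Scatterplots (8.6, 8.7).** Mark points by dose and fit a common within-dose slope.

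The SAP amendment is dated after database lock, so these results should be labelled as additions and shown beside the planned tests.

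**Cost.** SAP wording and one estimate statement per analysis. One degree of freedom is lost: about 0.5% in width at 8 + 8 if the doses do not differ. With equal weights and a common SD at 8 and 5 it is about 4%, and separate variances widen the interval further.
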